9.4 Intra-procedure Data Collection Requirements

1. Hemodynamic readings
2. ACT
3. AEs / SAEs
4. Times of pulse sprays administration
5. Time the r-tPA infusion(s) started
6. Time of heparin infusion(s) started
7. Technical complications
8. Medications
9. Equipment used
10. Blood pressure and heart rate, at start of procedure

9.5 Preparation in IR suite/Cath lab for Transfer to ICU

1. Suture sheaths in place.
2. Secure r-tPA and heparin drips to maintain infusions in the ICU.
3. Attach a 3-way stopcock and tubing to maintain patency and for continuous monitoring of the PA pressures in the ICU and an IV to keep open (TKO)

the central lumen (wire lumen) of the catheter per hospital standard protocol for each BEC.

4. Securing the device(s):
 - a. For CFV Access: tape device to thigh. Then follow step “e” below.
 - b. For IJ Access: Cover the catheter with a sterile sleeve (Such as the sleeve that comes with a Swan-Ganz catheter) tape device to left pectoral area with the shaft of the catheter placed posterior to the neck. Then follow step “5” below.
5. Place a strong adhesive dressing, such as Tegaderm™ (3M™, St Paul, MN) or equivalent tape over the handle and the actuator (slider) to make sure the handle and actuator (slider) are secure and cannot be moved.

10.0 POST-PROCEDURE PATIENT MANAGEMENT AND TESTS

The study subject will be admitted to the intensive care unit (ICU) where nursing staff are experienced in the care of patients treated for pulmonary embolisms.

10.1 r-TPA Infusion – Intensive Care Unit

1. **r-tPA Infusion:** Maintain the r-tPA Infusion through the infusion line on the side of the handle of the BEC in the ICU for approximately eight (8) hours from start of the infusion in the IR suite/Cath lab. The infusion should run at the rate prescribed in this protocol until the infusion is complete.
 - a. **Unilateral PE:** Infusion rate is to be maintained at 95cc/hour through the BEC, for a total of 1.27mg/hour infusing into the patient over approximately eight (8) hours. (95cc/hr= 1.27mg/hour x 1 infusion x approximately 8 hours = 10mg total). Infuse the r-tPA mixture until the infusion is complete.
 - b. **Bilateral PE:** Infusion rate is to be maintained at 0.65mg/hour through each catheter, for a total of 1.3mg/hour infusing into the patient (0.65mg/hour through each BEC). This is a rate of 65cc/hour per infusion for a total of 130cc/hour total infusing through two catheters into the patient. Infuse the r-tPA mixture until the infusion is complete
2. **Laboratory Tests:** Four (4) hours (\pm 1 hour) after initiation of heparin infusion started in the IR suite/Cath lab measure:
 - a. CBC
 - b. aPTT
3. **Hemodynamic Readings:** Record the following pressures in the ICU beginning with the 1st reading two (2) hours (\pm 30 minutes) after the initiation of the r-tPA infusion and then every thirty (30) minutes (\pm 15 minutes) thereafter through the central lumen of the BEC. If a waveform, or both waveforms (if bilateral) appear damped, verify each BEC pressure transducer is set up properly when study subject arrives in ICU. If the waveform continues to be damped, document the date and time when the waveform becomes phasic and print the waveform from the monitor. Mark on the waveform where the systolic PA, diastolic PA, and mean PA pressures are read and retain with the source documentation for this study. Please note that when the waveform becomes phasic, it must be documented even if it outside of the “every 30 minutes” scheduled readings. This is so the length of time from the 1st pulse spray (in the Cath/IR lab) to when the

clot dissolves in each PA with a pulmonary embolism will be known. Please note that printouts are not required for every reading, only when the damped waveform becomes phasic, if damped when subject arrives in the ICU. These readings are required through the completion of r-tPA infusion:

- a. PAS / PAD / PA Mean Pressures
- b. SpO₂ – Arterial Oxygen Saturation (pulse oximeter O₂ saturation)

4. **Mixed Venous Oxygen Saturation (SvO₂):** Record every two (2) hours (± 30 minutes) in the ICU starting after the initiation of the r-tPA infusion. These readings are required through the completion of r-tPA infusion:
 - a. SvO₂ – Mixed Venous Oxygen Saturations (Sample is from tip of the BEC, drawn from the central lumen of the BEC at the end of the handle. If bilateral, either BEC is acceptable for drawing the SvO₂.)
5. **Anticoagulation – Intensive Care Unit During r-tPA Infusion:** Heparin drip should be administered until the r-tPA infusion is complete (approximately 8 hours).
6. **Anti-coagulation Immediately Post-rtPA Infusion:** Once the r-tPA infusion is complete, turn off the heparin gtt. Starting 45 minutes (± 15 minutes) after the r-tPA completion, administer Lovenox 1mg/kg sub-Q every 12 hours (± 30 minutes) through the completion of the 48-hour CTA.
7. **Physical Exam:** A physical exam is required to be performed at the completion of the r-tPA infusion.
8. **Stopping r-tPA Infusion in ICU at the End of 8 Hours:** Upon completion of r-tPA infusion, maintain patency through the BEC by replacing r-tPA with heparinized saline using the infusion pump, at TKO, and transport to IR suite/Cath lab to remove BEC. Heparinized saline should infuse via infusion pump through the basket infusion port until subject arrives at the IR suite/Cath lab for catheter removal.

10.2 Return to The IR suite/Cath lab at The Completion of Infusion

At the end of the infusion the patient returns to the IR suite/Cath lab within eight (8) hours (+8 hours) of the completion of the r-tPA infusion for removal of the BEC(s) and final hemodynamic measurements.

1. Under fluoroscopy, collapse the basket(s) of the BEC.
2. Remove the BEC by pulling the catheter(s) carefully into the sheath(s) and then removing them from the body.
3. Back bleed or aspirate the sheath(s) and flush with heparinized saline to prevent clot formation.
4. **Catheter for Hemodynamic Readings and Blood Draws:** Insert a Swan-Ganz or angled pigtail catheter through the sheath and record the following.
 - a. **Hemodynamic Readings**
 - i. SvO₂ – Mixed Venous Oxygen Saturations
 - ii. SpO₂ – Arterial Oxygen Saturation (pulse oximeter)
 - iii. PA Pressures: PAS / PAD / PA Mean

- iv. CO – Modified Fick calculation (Refer to Terms and Definitions for required calculation)
- v. CI – Calculation

b. Fibrinogen – To be drawn at the time of the device removal in the IR suite/Cath lab. *The assay method must be recorded (e.g. Clauss, PT-derived fibrinogen assay, immunological, gravimetric, other)*

10.3 Tests Required at End of Infusion(s) and 24 Hours After r-tPA Infusion

10.3.1 Laboratory Tests and Other Tests

1. **BMP, CBC, Cardiac Biomarkers Troponin I and BNP** – These tests will be drawn 24 hours (± 8 hours) after completion of the r-tPA infusion.
2. **aPTT** – To be drawn once heparin gtt is stopped according to standard of care and ONLY IF it is standard of care to check aPTT after heparin gtt is discontinued.

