6.2.1 Primary Endpoints

1. Safety: Major bleeding, as defined by International Society of Thrombosis and Hemostasis (ISTH), within 72 hours of initiation of r-tPA administration. Bleeding criteria are as follows: Major Bleeding in Non-Surgical Patients.
 - a. Fatal bleeding; and/or
 - b. Symptomatic bleeding in a critical area or organ, such as intracranial, intraspinal, intraocular, retroperitoneal, intraarticular or pericardial, or intramuscular with compartment syndrome; and/or
 - c. Bleeding causing a fall in hemoglobin level of 2g/dL (1.24mmol/L) or more or leading to transfusion of two or more units of whole blood or red cells.²³
2. Feasibility: Device success defined as the ability to use the Bashir™ Endovascular Catheter as per this protocol.

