10.3.4 Data Collection

The following data will be collected and documented in the CRF in addition to the required pre-procedure testing.

1. **Medications** – All medications will be recorded that are administered within 24 hours following the infusion.
2. **Laboratory Test Results** – Tests performed above will be documented in the CRF.
3. **RV/LV End Diastolic Diameter Ratio** – This will be measured and calculated by echocardiogram at 24 hours (± 8 hours) following completion of the r-tPA infusion. The imaging will be sent to the independent core lab for analysis.

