10.5 Anticoagulation and Sheath Removal

10.5.1 Lovenox Administration

The subject must continue Lovenox 1mg/kg administered sub-Q every 12 hours (± 30 minutes) through the completion of the 48-hour CTA.

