10.6 Tests Required 72 Hours (+12 hours) Following Start of r-tPA Administration

10.6.1 Assessments

1. **AE/SAEs** – Adverse events will be monitored and reported on the CRF post-procedure through discharge. *Bleeding complications will be assessed through 72 hours (-4 / +12 Hours) following initial administration of the first r-tPA dose that was administered in the IR suite/Cath lab.*

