10.6.2 Data Collection

1. **Medications** – All medications will be recorded that are administered within 72 hours following the infusion.

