10.7 Tests Required Just Prior to Hospital Discharge

10.7.1 Assessments

1. **Physical Examination** – The physician will perform a physical examination within eight (8) hours (-8 Hours) of discharge.
2. **AE/SAEs** – Adverse events will be monitored and reported on the CRF post-procedure through discharge.
3. **12-Lead Electrocardiogram** – To be done prior to and no greater than within eight (8) hours (-8 Hours) prior to discharge.

11.0 30-DAY FOLLOW-UP VISIT POST PROCEDURE

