21.0 APPENDICES

APPENDIX 21.1 REQUIRED STUDY PROCEDURES

Test	Pre-Procedure	Procedure	Post-Procedure	End of Infusion	24 Hrs Post-r-tPA Completion	48 Hrs Post-r-tPA Completion	72 Hrs Post- r-tPA Initiated	Before Discharge	30-day Follow-up
Visit Window	≤ 48 Hrs of procedure			+8 Hrs	± 8 Hrs	± 6 Hrs	-4 / +12 Hrs	-8 Hrs	± 7 Days
Informed Consent	X								
Demographics and Medical History	X								
Physical Examination	X			X	X			X	X
12 Lead ECG	X							X	
CBC, INR ¹	X		X ²		X				
aPTT	X ²		X	X					
Fibrinogen ³	X			X					
CMP	X								
BMP					X				
Cardiac Biomarkers: Troponin I, BNP	X				X				
Lower Extremity Venous DUS	X								
Contrast Enhanced CTA of the Chest	X						X		
RV/LV Diameter Ratio with each CTA	X						X		
Echocardiogram	X				X				
RV/LV Diameter Ratio with each Echocardiogram	X				X				
Eligibility Criteria	X	X							
Anticoagulation ³ (Heparin, Lovenox)	X	X	X	X	X	X			
IR / Cath Lab: Invasive Hemodynamic Data / ACT ⁴		X		X					
IR / Cath Lab: r-tPA Pulse Sprays Administration		X							
Bashir™ Endovascular Catheter(s) and r-tPA Use ⁵		X	X	X					
ICU: PAS / PAD / Mean PA q 30 Min via BEC			X	X					
ICU: Mixed venous SvO ₂ q2 Hours via BEC			X	X					
r-tPA Infusion		X	X						
Medications	X	X	X	X	X	X	X	X	X
AEs / SAEs		X	X	X	X	X	X	X	X
Contrast Enhanced CTs to Core Lab	X					X			
Echocardiograms to Core Lab	X				X				

¹INR is only required at baseline for patients on Coumadin (warfarin) and must be ≤ 1.5 prior to enrollment. If patient is eligible for the study, Coumadin will be discontinued temporarily for study purposes.

[figure not shown]
²Pre-procedure suggested aPTT 60-80s. Suggested aPTT during r-tPA administration is 40-60s. Check aPTT and CBC 4 hr (± 1 hr) after heparin is restarted in the IR suite/Cath lab (suggested range 60-80s).

[figure not shown]
³Unfractionated Heparin will be infused IV pre-procedure or Lovenox. Stop Heparin prior to start of procedure. Restart Heparin post procedure with r-tPA infusion. Fibrinogen to be drawn at time of BEC removal in IR suite/Cath lab. Heparin infusion will continue until the completion of the r-tPA infusion. Lovenox 1mg/kg Sub-Q will be started 45 minutes (± 15 minutes) from the completion of the r-tPA infusion and given q12hrs (± 30 min).

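### The primary safety endpoint counts bleeding with a haemoglobin fall of 2 g/dL or more up to 72 h, but the last required blood count is at about 24-40 h

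*Combined protocol and SAP*

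**What the plan says.** Section 6.2.1 defines the primary safety endpoint as ISTH major bleeding within 72 h of r-tPA initiation. Its third criterion includes "Bleeding causing a fall in hemoglobin level of 2g/dL (1.24mmol/L) or more".

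A CBC is required at three times:

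- within 48 h before the procedure (Section 7.1.1);
- early after treatment (Section 10.1). Appendix 21.1 puts it as "Check aPTT and CBC 4 hr (± 1 hr) after heparin is restarted in the IR suite/Cath lab";
- about a day after the infusion ends (Section 10.3.1): "These tests will be drawn 24 hours (± 8 hours) after completion of the r-tPA infusion".

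The CBC row of Appendix 21.1 marks the same three columns. Later sections list no haemoglobin:

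- Section 10.4 (48 h) has the CTA, adverse events and medications.
- Section 10.6 (72 h) says "Bleeding complications will be assessed through 72 hours (-4 / +12 Hours) following initial administration of the first r-tPA dose" but names no laboratory test. Its data collection item is "All medications will be recorded that are administered within 72 hours following the infusion".
- Section 10.7 (discharge) has a physical examination, adverse events and an ECG.

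For the 24-hour laboratory results, Section 10.3.4 says "Tests performed above will be documented in the CRF". Sections 10.4.3 and 10.6.2 have no matching item. Section 10.5.1 keeps subjects on Lovenox "through the completion of the 48-hour CTA".

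**The concern.** A fall of 2 g/dL can be established only by measuring haemoglobin, and the required measurements stop well before the endpoint window closes. Anticoagulation continues after the last one. For a bleed in that interval that meets the definition only through the fall, the classification depends on whether the site happens to draw a CBC. The protocol has no rule requiring one when bleeding is suspected.

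Major bleeding is the main safety result of a first-in-man study of up to 10 subjects at up to five sites. It is reported descriptively and is meant to inform a pivotal trial (Sections 16.1 and 16.2). In a sample this small, one event counted or not counted visibly changes the reported rate.

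**Working it through.** **Inputs.** Infusion volumes and rates: 750 cc at 95 cc/h (unilateral) and 500 cc at 65 cc/h per catheter (bilateral), from Table 2. Last CBC: 24 ± 8 h after completion (10.3.1). Catheter removal: within 8 h (+8 h) of completion (10.2). CTA: 48 ± 6 h after completion (10.4.1). 72-hour assessment: -4/+12 h, that is 68-84 h from the first dose (10.6.1). Endpoint window: 72 h from start (6.2.1).

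**Infusion duration.** Section 4.3 gives 7.87 h for unilateral PE. This reproduces: 10 mg / 1.27 mg/h = 7.87 h, and by volume 750/95 = 7.89 h. Bilateral: 500/65 = 7.69 h. The pause for pulse sprays adds a short unstated time that does not alter the result.

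**Last required CBC, from r-tPA start** = duration + 24 h (± 8 h):

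- earliest: 7.7 + 16 = 23.7 h
- nominal: 31.7 h (bilateral) to 31.9 h (unilateral)
- latest: 7.9 + 32 = 39.9 h

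**Window left after that CBC:**

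| Timing of last CBC | Hours left to 72 h | Share of window |
|---|---|---|
| latest | 72 - 39.9 = 32.1 | 44.6% |
| nominal | 40.1-40.3 | 55.7-56.0% |
| earliest | 72 - 23.7 = 48.3 | 67.1% |

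**Anticoagulation after that CBC.** The CTA falls at 42-54 h after completion, or 49.7-61.9 h from start. From last CBC to CTA is 42 - 32 = 10 h at least, 54 - 16 = 38 h at most, and 48 - 24 = 24 h nominally.

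**Other possible haemoglobin values.** The modified Fick formula needs a haemoglobin, and cardiac output is measured again when the catheter is removed. The latest removal is 8 + 8 = 16 h after completion, or 23.7-23.9 h from start. That coincides with the earliest permitted time for the last CBC, so it does not extend coverage.

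**Interval to the 72-hour assessment.** 68 - 39.9 = 28.1 h to 84 - 23.7 = 60.3 h after the last CBC.

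**Effect of one event in 10 subjects (Clopper-Pearson 95%).** 1/10: 0.3-44.5%. 0/10: 0-30.8%.

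**With a CBC at the 72-hour assessment.** It would be drawn at 68-84 h, so the uncovered tail is 0-4 h, at most 4/72 = 5.6%. If a subject is discharged straight after the CTA (an assumption, since discharge time is not given), a discharge CBC leaves 72 - 61.9 = 10.1 h to 72 - 49.7 = 22.3 h.

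**The case against.** The strongest reply is that the exposed group is narrow. Fatal bleeding, symptomatic critical-site bleeding and transfusion of two or more units need no later CBC. Section 13.3 sends all adverse events to the CRF, Table 3 lists hemorrhage with a haemoglobin decrease, Table 5 lists anemia, Section 10.6.1 requires a bleeding review, and the data safety monitor adjudicates (17.0). A recognised late bleed would probably still be recorded, at least as clinically relevant non-major bleeding (secondary endpoint 5). All r-tPA is finished by about 8 h, and catheter removal is due no later than the last CBC. The 45-67% is clock time, the analysis is descriptive, and the numeric safety rule in Section 18.2 (death or intracranial haemorrhage) is untouched. The CRF and safety charter are separate documents and may ask for more, and Section 14.1 requires site records to hold diagnostic results.

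Most of this stands and limits the size of the point. It does not close the gap. These provisions record the bleed, but they do not supply the value that decides whether it is major. A late bleed filed as non-major for want of a haemoglobin is still lost from the primary endpoint.

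A second objection is that a difference between baseline and the lowest value may include dilution from infused fluid, and that the baseline value may be up to 48 h old. Dilution alone cannot create an event, because the definition requires bleeding to cause the fall. The age of the baseline value is a reason to say which value is used.

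**Conclusion.** The concern holds. The last required haemoglobin is at 23.7-39.9 h, which leaves 32-48 h of the 72 h endpoint window without one, and Lovenox continues for 10-38 h of that time. The exposure is limited to a bleed after the last CBC that meets the definition only by the 2 g/dL fall and is either not evident or not followed by a local CBC.

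The documents give no frequency for such bleeds, so no probability of a miss is claimed. The 1/10 against 0/10 comparison shows what one such event would do, not how likely it is. The conclusion rests on the protocol's stated rates and windows, and on the CRF and safety charter, which were not available, adding no later CBC. No power figure or numeric stopping rule is affected. It should be fixed because it concerns the primary safety endpoint and costs little to correct.

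**What to change.** 1. In Section 10.6 and Appendix 21.1, add a CBC at the existing 72-hour (-4/+12 h) assessment, or at discharge if that is earlier. The discharge option narrows the gap without closing it, as the figures above show.
2. In Sections 10.4.3 and 10.6.2, require every local haemoglobin value through that assessment to be entered in the CRF.
3. In Section 6.2.1, define the fall as the pre-procedure value minus the lowest value through that assessment, and say which pre-procedure value is used if there are several. State that a value drawn after 72 h counts only if the bleeding began within 72 h.

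The requirement that bleeding cause the fall, and adjudication by the data safety monitor, stay as they are.

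The cost is one routine blood count per subject (about 10 in all) and some CRF fields, more of them where a site draws repeated counts. The observed bleeding rate may come out slightly higher.

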10.3.2 Imaging

1. **Echocardiogram** – The echocardiogram will be done to determine the RV/LV end-diastolic diameter ratio at 24 hours (± 8 hours) from the completion of the r-tPA infusion. A core lab protocol will be followed for data acquisition. *The echocardiogram will be sent to the core lab for analyses.*

10.3.3 Assessments

1. **Physical Examination** – The physician will perform a physical examination at the end of the infusion and 24 hours (± 8 Hours) after completion of r-tPA infusion.
2. **AE/SAEs** – Adverse events will be monitored and reported on the CRF post-procedure through 24 hours.

10.3.4 Data Collection

The following data will be collected and documented in the CRF in addition to the required pre-procedure testing.

1. **Medications** – All medications will be recorded that are administered within 24 hours following the infusion.
2. **Laboratory Test Results** – Tests performed above will be documented in the CRF.
3. **RV/LV End Diastolic Diameter Ratio** – This will be measured and calculated by echocardiogram at 24 hours (± 8 hours) following completion of the r-tPA infusion. The imaging will be sent to the independent core lab for analysis.

10.4 Tests Required 48 Hours Following End of r-tPA Infusion

10.4.1 Imaging

1. **Contrast Enhanced CTA of the Chest** – A contrast enhanced chest CTA will be performed at 48 hours (± 6 hours) after completion of the r-tPA infusion. The contrast enhanced chest CTA is used to determine the post-procedure RV/LV diameter ratio and Modified Miller Index Score. Please note that subject must be on Lovenox 1mg/kg every 12 hours through the completion of the 48-hour CTA. *The CT will be sent to the core lab for analyses.*

10.4.2 Assessments

1. **AE/SAEs** – Adverse events will be monitored and reported on the CRF post-procedure through 48 hours.

10.4.3 Data Collection

1. **Medications** – All medications will be recorded that are administered within 48 hours following the infusion completion.
2. **RV/LV End Diastolic Diameter Ratio** – This will be measured and calculated by CTA at 48 hours (± 6 hours) following completion of the r-tPA infusion. The imaging will be sent to the independent core lab for analysis.
3. **Modified Miller Index Score** – This will be documented by the core lab after the contrast-enhanced chest CTA is performed. This will also be performed by the independent core lab.

10.5 Anticoagulation and Sheath Removal

10.5.1 Lovenox Administration

The subject must continue Lovenox 1mg/kg administered sub-Q every 12 hours (± 30 minutes) through the completion of the 48-hour CTA.

10.5.2 FDA Approved Anticoagulation Regimen

At the time of r-tPA infusion completion and through the completion of the 48-hour CTA, administer Lovenox 1mg/kg subcutaneously. Study subjects may be prescribed any FDA approved regimen of anticoagulation after the 48-hour CTA scan is complete. The long-term anticoagulation administration is according to the physician's discretion.

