ANTICOAGULANT DOSAGE AND ADMINISTRATION	
Pre-procedure: Unfractionated heparin will be administered IV to prolong the aPTT pre-procedure (suggested range 60-80 seconds).
 
Note: Use of enoxaparin (Lovenox®) is permitted pre-procedure for the treatment of PE. If Lovenox is given, then catheter directed thrombolysis procedure is to start no sooner than 12 hours after the last Lovenox dose was administered.
 
Procedure: Heparin infusion will be discontinued upon arrival in the IR/Cath lab. ACT will be monitored in IR/Cath Lab and heparin boluses administered to achieve ACT \geq 200 seconds.
 
During r-tPA Infusion: Heparin infusion will be restarted post-procedure and administered through the side arm of each sheath to prolong the aPTT (suggested range 40-60 seconds).
 
Post r-tPA Infusion: Upon completion of r-tPA infusion, maintain patency through the BEC by replacing r-tPA with heparinized saline TKO using the infusion pump. Starting 45 minutes (\pm 15 minutes) after the r-tPA completion, administer Lovenox 1mg/kg sub-Q every 12 hours (\pm30 minutes) through the completion of the 48-hour CTA.

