- k. Ensure the BEC(s) are adequately flushed. Attach the flushed pressure transducer tubing to the wire lumen of the BEC(s). Measure the systolic PA, diastolic PA, and mean PA pressures in each PA with a pulmonary embolism from the tip of the BEC through the guidewire lumen at the back of the BEC handle. Print the PA waveform tracings and mark the tracings where the systolic PA, diastolic PA, and mean PA pressures are interpreted and documented.
- l. If the waveform is damped, adequately flush the wire lumen. If the waveform is still damped after it is flushed, print the damped waveform on paper, and retain the waveform with the source documentation for this study. Measure the systolic PA, diastolic PA, and mean PA pressures in each PA with a pulmonary embolism on the tracing. If the waveform becomes phasic prior to leaving the lab, print the waveform, mark on the waveform where the systolic PA, diastolic PA, and mean PA pressures are interpreted and the time the waveform became phasic. Retain the printout with the source documentation for this study.

9.3.2 Part 2 – r-tPA Infusion and Anticoagulation – Prior to Departing the IR suite/Cath lab r-tPA Infusion

Upon completion of the Pulse Sprays, with the basket re-expanded and catheter securely in place, begin r-tPA solution infusion(s), as soon as possible (immediately following the pulse sprays).

1. **For unilateral PE:** The total r-tPA is 10mg at 1.27mg/hr. Using an IV pump at 95cc/hour, infuse the 750cc of 0.9% NaCl with the 10mg r-tPA at 1.27mg/hr until infusion is complete (approximately 8 hours).
2. **For bilateral PE:** The total r-tPA dose is 10mg at 1.30mg/hr. Using two (2) IV pumps at 65cc/hour, infuse the 500cc of 0.9% NaCl x 2 simultaneously with the 5mg r-tPA at 0.65mg/hr for each PE for a total of 1.3mg/hour until complete (approximately 8 hours).
3. **Anticoagulation:** Re-start low dose heparin infusion into each sheath to prolong the aPTT (suggested range 40 to 60 seconds) prior to leaving the

IR suite/Cath lab to maintain therapeutic dose through completion of the 48-hour CT scan.

The institution is to follow the standard of care for the administration of heparin and the monitoring of aPTT in addition to the aPTTs measured at certain time points required by this protocol.

4. **Maintaining Patency Through the Central Lumen of the BEC(s):**

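### Section 10.5.2 gives Lovenox at r-tPA completion, but the synopsis, Section 10.1 and Appendix 21.1 start it 45 (±15) minutes later, and nothing says which text governs

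*Combined protocol and SAP*

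**What the plan says.** Four places in the current protocol set the start of Lovenox after r-tPA.

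- Section 10.5.2: "At the time of r-tPA infusion completion and through the completion of the 48-hour CTA, administer Lovenox 1mg/kg subcutaneously". It states no delay and no window, and refers to no other section.
- Section 10.1 item 6: "Starting 45 minutes (± 15 minutes) after the r-tPA completion, administer Lovenox 1mg/kg sub-Q every 12 hours".
- The synopsis, under anticoagulant dosage, gives the same delay and the same window as Section 10.1.
- Appendix 21.1 footnote 3: "Lovenox 1mg/kg Sub-Q will be started 45 minutes (± 15 minutes) from the completion of the r-tPA infusion".

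The dose is 1 mg/kg in all four. Section 10.5.1, directly above 10.5.2, adds the dosing interval but no start: "The subject must continue Lovenox 1mg/kg administered sub-Q every 12 hours (± 30 minutes) through the completion of the 48-hour CTA".

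The primary safety endpoint in Section 6.2.1 is ISTH major bleeding "within 72 hours of initiation of r-tPA administration".

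The end of the heparin infusion is also stated in two ways. Section 9.3.2 item 3 carries it on until the 48-hour CT scan is done. Section 7.1.4 and Section 10.1 items 5 and 6 stop it when the r-tPA infusion completes.

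**The concern.** The first Lovenox dose marks the change from the infusions to subcutaneous anticoagulation, and it is given while major bleeding is being counted for the primary endpoint. The protocol sets a tolerance of ±15 minutes on its start, so it treats the timing as something to control. Section 10.5.2 gives a time outside that tolerance.

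With up to five sites, staff may look up anticoagulation in different sections. Some could dose at completion and others 30 to 60 minutes later, each following current text. A dose given as 10.5.2 reads would also be out of window under the other three places. Section 14.1 item 12 does not permit deviations except to protect the patient, so monitors would need to know which text to apply.

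**Working it through.** **1. When r-tPA completes.** The inputs are in Section 9.3.2. Unilateral PE: "Using an IV pump at 95cc/hour, infuse the 750cc of 0.9% NaCl with the 10mg r-tPA at 1.27mg/hr until infusion is complete". Bilateral PE: "Using two (2) IV pumps at 65cc/hour, infuse the 500cc of 0.9% NaCl x 2 simultaneously". Duration = bag volume / pump rate.

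- Unilateral: 750 / 95 = 7.89 h
- Bilateral: 500 / 65 = 7.69 h

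Both reproduce the protocol's own figure of approximately 8 hours. They are pump-running times. Section 9.2 starts the pump before the catheter enters the sheath, and Section 9.3.1 pauses it for the pulse sprays, so elapsed time from pump start to completion is at least this long.

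**2. When the first Lovenox dose falls.** Hours are counted from pump start with no pause. Section 10.5.2 adds 0 h. The other three places add 45 ± 15 min, which is 0.5 to 1.0 h.

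| | Section 10.5.2 | Synopsis, 10.1 item 6, Appendix 21.1 |
|---|---|---|
| Unilateral | 7.89 h | 8.39 to 8.89 h |
| Bilateral | 7.69 h | 8.19 to 8.69 h |

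Within each row the times do not overlap. The smallest gap is 30 minutes and the largest 60. Pump pauses move both columns equally and leave the gap unchanged.

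**3. Position in the bleeding window.** Time left of the 72 h, taking pump start as zero:

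- Unilateral: 72 − 7.89 = 64.11 h under 10.5.2, and 72 − 8.89 = 63.11 h at the latest time elsewhere.
- Bilateral: 72 − 7.69 = 64.31 h, and 72 − 8.69 = 63.31 h.

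On either text the dose falls early in the window. The gap is 0.5/72 = 0.7% to 1.0/72 = 1.4% of it.

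**4. Whether other text settles it.** Section 10.5.1 speaks of continuing Lovenox and gives the 12-hour interval, so it assumes a start set elsewhere. No section ranks one text above another. As background only, the version table says version 6.0 specified the window for starting Lovenox, and its version 5.0 entry has Lovenox given at r-tPA completion. That would fit 10.5.2 not having been updated, but the contradiction rests on the four current sections and not on the log.

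**5. Heparin.** Section 9.3.2 item 3 and Sections 7.1.4 and 10.1 cannot both be followed. The CTA is due 48 hours (±6) after r-tPA completion, so the two end points for heparin lie 42 to 54 hours apart. This conflict is much longer than the Lovenox one and concerns the same handover.

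**The case against.** The best case for the plan is that 10.5.2 describes a period and does not set a clock time. Its heading and its remaining sentences concern which anticoagulant is required up to the 48-hour CTA and what is allowed afterwards. The bedside step is Section 10.1 item 6, which is more specific and is matched by the synopsis and the schedule footnote. A site would have to overlook three agreeing texts to dose from 10.5.2 alone. This stands as a reason to expect most sites to use the 45-minute text. It does not remove the contradiction: 10.5.2 is worded as an instruction to administer, names completion as the time, and points to no other section.

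A reader might infer more than the documents support:

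- **Overlapping anticoagulation under 10.5.2.** The documents give no onset or clearance data for heparin, r-tPA or enoxaparin, and do not say what an interval of 30 to 60 minutes achieves.
- **A number of patients affected.** Nothing indicates how many sites would follow which section.
- **Deviation in both directions.** A dose at completion is outside the 30-to-60-minute window. The reverse is unclear, because 10.5.2 states no window to breach.
- **A missing dosing interval.** Section 10.5.1 supplies it, directly above.
- **No record of the first-dose time.** The case report form is a separate document that was not supplied, and the protocol already requires medications to be recorded over the first 24, 48 and 72 hours. Whether a time field exists cannot be checked.

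**Conclusion.** The inconsistency is real and is in operative text. Section 10.5.2 places the first Lovenox dose 30 to 60 minutes before the other three places do, and at least 30 minutes before the earliest time they allow, inside the primary bleeding window. The hours after pump start are minimum values, and they assume that the 72-hour clock and the pump start together. A different zero would shift those hours but not the gap.

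The consequence is modest. One might infer that the bleeding result would be distorted, but no such effect can be derived from the documents. It is likely small in a ten-subject study that Section 16.2 describes as descriptive and not powered for its primary endpoints. Sample size and analysis are unaffected. What remains is a treatment instruction that sites could carry out differently, with one of the two readings falling outside the stated window. Nothing here bears on which timing is clinically right.

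**What to change.** Reconcile Section 10.5.2 with the synopsis, Section 10.1 item 6 and Appendix 21.1 footnote 3, so that one start time and one window apply throughout. Alternatively, have 10.5.2 refer to a single governing section and state no time of its own. In the same edit, reconcile Section 9.3.2 item 3 with Sections 7.1.4 and 10.1 on when the heparin infusion ends. The choice of timing in both cases belongs to the sponsor's clinicians.

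The cost is a sentence or two of protocol text in an amendment and a notice to the sites. Endpoints, sample size and analysis do not change.
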